4.2. Secondary Objectives

The secondary objectives of the study are the following:

Table JAIV.4.2. Secondary Objectives and Endpoints

Objectives	Endpoints

 To evaluate the effect of baricitinib 4-mg QD compared to placebo on PBC disease 	
 Proportion of patients with ALP <1.67 x ULN (and at least 15% decrease from baseline) and total bilirubin <ULN at Week 12

 To evaluate the effect of baricitinib 2-mg QD compared to placebo on PBC disease 	
 Change from baseline in ALP at Week 12 Proportion of patients with ALP <1.67 x ULN (and at least 15% decrease from baseline) and total bilirubin < ULN at Week 12

 To evaluate the effect of baricitinib 4-mg and 2-mg QD compared to placebo on PBC symptoms 	
 Change from baseline in itch as measured by Itch NRS at Week 12 Change from baseline in fatigue as measured by Fatigue NRS at Week 12

[figure not shown]
Abbreviations: ALP = alkaline phosphatase; NRS = Numeric Rating Scale; PBC = primary biliary cholangitis; QD = once daily; ULN = upper limit of normal.

5. Study Design

5.1. Summary of Study Design

Study JAIV is a multicenter, randomized, double-blind, parallel, placebo-controlled, proof-of-concept, Phase II study in patients with primary biliary cholangitis (PBC) who have an inadequate response or are intolerant to UDCA. The study will be conducted in 2 cohorts. Cohort A will randomize patients to placebo and baricitinib 2-mg. Cohort B will randomize patients to placebo and baricitinib 4-mg. Enrollment in Cohort B will begin only after the data monitoring committee (DMC) review of Cohort A is complete and Lilly has received and accepted a recommendation to proceed. Both cohorts will follow the same study schedule.

Figure JAIV.5.1 illustrates the study design.

Abbreviations: V = Visit; W = Week.

^a Patients able to tolerate ursodeoxycholic acid (UDCA) will take UDCA orally as background therapy during the study.

Figure JAIV.5.1.

Illustration of study design for Clinical Protocol I4V-MC-JAIV.

Patients in Cohort A and Cohort B will follow the same study schedule as outlined in this figure. Cohort A will randomize 12 patients to baricitinib 2-mg and 8 patients to placebo. After a DMC review of Cohort A data, Cohort B will then randomize 20 patients to baricitinib 4-mg and 12 patients to placebo.

5.2. Determination of Sample Size

Approximately 20 patients will be randomized to the baricitinib 2-mg and placebo treatment groups for Cohort A. Twelve patients will be randomly assigned to the 2-mg treatment group and 8 patients to the placebo treatment group. This sample size is appropriate to provide

sufficient preliminary safety and tolerability information for baricitinib 2-mg in patients with PBC prior to studying 4-mg baricitinib.

For Cohort B, 32 patients will be randomized to the baricitinib 4-mg and placebo treatment groups. Twenty patients will be randomized to the baricitinib 4-mg treatment group and 12 patients to placebo.

Overall, 20 patients per group will be assigned to the baricitinib 4-mg (Cohort B) and placebo (Cohorts A and B) dose groups. Based on this sample size, this study will have approximately 81% power to detect a difference in ALP change from baseline between baricitinib 4-mg and placebo at Week 12 assuming that the true difference is 65 U/L. The sample size was determined based on a 2-sample t-test with 2-sided alpha level of 0.1 and a standard deviation of 80 U/L for the change from baseline in ALP. The sample size calculation was performed using nQuery[®] Advisor 7.0 software.

5.3. Method of Assignment to Treatment

[REDACTED]

[REDACTED]

Assignment to treatment groups will be determined by a computer-generated random sequence using an interactive web-response system (IWRS). The IWRS will be used to assign double-blind investigational product to each patient. Site personnel will confirm that they have located the correct package by entering a confirmation number found on the package into the IWRS.

6. A Priori Statistical Methods

6.1. General Considerations

This plan describes *a priori* statistical analyses for efficacy, health outcome, and safety that will be performed.

Statistical analysis of this study will be the responsibility of Eli Lilly and Company (Lilly) or its designee. The statistical analyses will be performed using SAS[®] Version 9.4 or a more recent version.

Not all displays described in this SAP will necessarily be included in the clinical study report (CSR). Not all displays will necessarily be created as a “static” display. Some may be incorporated into interactive display tools instead of or in addition to a static display. Any display described in this SAP and not included in the CSR would be available upon request.

Incidence rates and 95% confidence interval (CI) will be displayed for select safety endpoints.

Statistical tests of treatment effects and CIs will be performed at a 2-sided significance level of 0.1, unless otherwise stated. No multiplicity adjustment will be used in this study.

Data collected at early termination visits will be mapped to the next scheduled visit number for that patient if it falls within the visit window. For by-visit summaries, only visits in which a measure was scheduled to be collected will be summarized. Any unscheduled visit data will be included at the patient-level listings. However, the data will be included in other analyses, including shift analyses for safety analytes, change from baseline to endpoint using last observation carried forward (LOCF) analyses, and other categorical analyses.

6.1.1. Analysis Populations

Modified intent-to-treat (mITT) population: The mITT population is defined as all randomized patients who take at least 1 dose of investigational product

Safety population: The safety population is defined as all randomized patients who receive at least 1 dose of investigational product and who did not discontinue from the study for the reason “lost to follow-up” at the first postbaseline visit.

Unless otherwise specified, the efficacy and health outcome analyses will be conducted on the mITT population. Patients will be analyzed according to the treatment to which they were randomized. The analysis populations will include patients from both Cohort A and Cohort B.

Concomitant medications will be descriptively summarized by treatment group in terms of frequencies and percentages using the safety population. The medications will be coded accordingly.

All safety data will also be descriptively summarized by treatment groups and analyzed using the safety population.

In the rare situation where a patient is lost to follow-up at the first postbaseline visit, but some safety data exist (e.g., unscheduled laboratory assessments) after first dose of study drug, a listing of the data or a patient profile will be provided.

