10.2. Populations for Analyses

For purposes of analysis, the following populations are defined:

Population	Description
Enrolled	All patients who sign informed consent
Randomized	All patients who are randomized at Week 0.
Modified Intent-to-Treat (mITT)	The mITT population is defined as all randomized patients who take at least one dose of study treatment. Patients will be included if they do not receive the correct treatment, or otherwise do not follow the protocol. Subjects will be analyzed according to the treatment to which they were randomized.
Safety	The safety population is defined as all randomized patients who receive at least 1 dose of study treatment and who did not discontinue from the study for the reason 'Lost to Follow-up' at the first postbaseline visit with no safety post-baseline data. Patients will be analyzed according to the treatment to which they were randomized.

Additional subpopulations may be identified. Full details will be provided in the study statistical analysis plan (SAP).

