10.3. Statistical Analyses

10.3.1. General Statistical Considerations

Statistical analysis of this study will be the responsibility of Lilly or its designee.

Unless otherwise specified, the efficacy, health outcomes, and safety analyses will be conducted on the modified intent-to-treat (mITT) population.

All tests of treatment effects will be conducted at a 2-sided alpha level of 0.1, unless otherwise stated. No multiplicity adjustment will be used in this study.

Baseline will be defined as the last available value before the first dose of investigational product for both efficacy and safety analyses. In most cases, this will be the measure recorded at Week 0 (Visit 3). Change from baseline will be calculated as the visit value of interest minus the baseline value.

Any change to the data analysis methods described in the protocol will require an amendment ONLY if it changes a principal feature of the protocol. Any other change to the data analysis methods described in the protocol, and the justification for making the change, will be described in the clinical study report (CSR). Additional exploratory analyses of the data will be conducted as deemed appropriate.

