6.15. Protocol Violations

Protocol deviations will be tracked by the clinical team, and their importance will be assessed by key team members during protocol deviation review meetings.

Potential examples of deviations include patients who receive excluded concomitant therapy, significant non-compliance with study medication (<80% of assigned doses taken, failure to take study medication and taking incorrect study medication), patients incorrectly enrolled in the study, and patients whose data are questionable due to significant site quality or compliance issues. Refer to a separate document for the important protocol deviations.

The number and percentage of patients having IPD(s) will be summarized within category and subcategory of deviation by treatment group for Period 2 using the ITT population. Individual patient listings of IPDs will be provided.

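### The SAP's safety population leaves out an early lost-to-follow-up patient with safety data whom the protocol keeps, and neither document provides for analysing safety by treatment received

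*SAP*

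**What the plan says.** **Who is in the safety population**

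- Protocol 10.2 removes a dosed patient only if that patient was lost to follow-up "at the first postbaseline visit with no safety post-baseline data".
- SAP 6.1.1 counts "all randomized patients who receive at least 1 dose of investigational product and who did not discontinue from the study for the reason" of loss to follow-up at the first postbaseline visit. It sets no condition about whether safety data exist.
- The same SAP section then takes up the case of a patient lost that early who does have safety information after dosing. For that patient it says only that "a listing of the data or a patient profile will be provided".
- SAP section 3 says the SAP is based on protocol amendment (b). It gives no reason for the different definition.

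**Which treatment the patient is counted under**

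- Protocol 10.2 puts the as-randomised rule inside the safety population definition itself.
- SAP 6.1.1 states "Patients will be analyzed according to the treatment to which they were randomized". The sentence follows the one on efficacy and health outcomes, and no other rule is given for safety.
- Protocol 10.2, under mITT, says "Patients will be included if they do not receive the correct treatment". SAP 6.15 names "taking incorrect study medication" among possible deviations.

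**Where the population is used**

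- Both safety analysis sets in SAP Table JAIV.6.6 are built on it, and so are most safety tables and the Fisher and ANCOVA comparisons in SAP 6.13.
- Table JAIV.6.7 lists deaths and SAEs on the Enrolled set instead.

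**The concern.** A patient who takes the drug, has an abnormal laboratory result or an adverse event, and then disappears may have left because of tolerability. Under the SAP that patient leaves the numerator and the denominator together, so the tables show neither the event nor a gap. With 12 to 20 patients per group, one such patient visibly changes an event rate. The protocol, which the SAP is meant to implement, would have kept the patient.

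The as-randomised rule raises a related problem. A patient who took another arm's treatment has the resulting events counted against a treatment not taken. In a safety comparison this tends to hide a difference.

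**Working it through.** **1. The plan's own figure.** The only computed design figure is the power for 4 mg against placebo: 20 per group, difference 65 U/L, SD 80 U/L, two-sided alpha 0.1 (protocol 10.1, SAP 5.2). The noncentrality is 65 / (80 × √(2/20)) = 2.57 on 38 degrees of freedom, which gives 81.0% against the stated 81%. The primary analysis uses mITT, so this point does not touch it.

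**2. The two definitions side by side.**

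| Dosed patient | Protocol 10.2 | SAP 6.1.1 |
|---|---|---|
| Not lost to follow-up at the first postbaseline visit | in | in |
| Lost at that visit, no postbaseline safety data | out | out |
| Lost at that visit, some postbaseline safety data | **in** | **out** (listing or profile) |

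The documents differ only in the third row. The SAP's own sentence on that case shows that it is a real exclusion and not shortened wording.

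**3. What one patient does to a rate.** Group sizes are 12 (2 mg) and 20 (4 mg), from protocol 5.2. Assume the one excluded patient had the event. The rate x/n becomes (x − 1)/(n − 1). Upper limits are exact (Clopper–Pearson) two-sided 95%.

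| Arm | Protocol | SAP | Upper limit, protocol | Upper limit, SAP |
|---|---|---|---|---|
| 2 mg, x = 1 | 1/12 = 8.3% | 0/11 = 0% | 38.5% | 28.5% |
| 2 mg, x = 2 | 2/12 = 16.7% | 1/11 = 9.1% | 48.4% | 41.3% |
| 4 mg, x = 1 | 1/20 = 5.0% | 0/19 = 0% | 24.9% | 17.6% |
| 4 mg, x = 2 | 2/20 = 10.0% | 1/19 = 5.3% | 31.7% | 26.0% |

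**4. What it does to the test.** The two-sided Fisher p-value need not move. Against 0/20 on placebo, 4/20 gives p = 0.106 and 3/19 gives p = 0.106; 5/20 and 4/19 both give p = 0.047. In these examples the harm is to the rate and its upper limit, not to the p-value.

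**5. As randomised against as treated.** Assume one placebo patient took 4 mg and had an event, and e patients randomised to 4 mg also had one. As randomised the comparison is e/20 against 1/20; as treated it is (e + 1)/21 against 0/19.

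| e | As randomised | Fisher p | As treated | Fisher p |
|---|---|---|---|---|
| 0 | 0/20 vs 1/20 | 1.00 | 1/21 vs 0/19 | 1.00 |
| 2 | 2/20 vs 1/20 | 1.00 | 3/21 vs 0/19 | 0.23 |
| 4 | 4/20 vs 1/20 | 0.34 | 5/21 vs 0/19 | 0.049 |

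SAP 6.13 describes p ≤ 0.05 as strong statistical evidence of a difference. In the last row the assignment rule alone decides whether that label applies. All event counts in steps 3 to 5 are assumptions.

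**The case against.** The case for leaving the plan alone is that little can be lost:

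- The SAP calls the situation rare. The first postbaseline visit is at Week 1, and protocol 8.3 requires repeated failure to return and failed contact before a patient counts as lost. A patient whose recorded reason for stopping is an adverse event stays in the safety population.
- Nothing is deleted. The data appear in a listing or profile, deaths and SAEs are listed on the Enrolled set, and disposition uses mITT (SAP 6.6).
- On wrong treatment, each cohort has one active dose, and sites confirm the package number in the IWRS (protocol 7.2).

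All of this stands, and it limits the point to non-serious events, laboratory summaries, rates and tests. It does not explain why the SAP should exclude a patient whom the protocol includes.

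Four stronger readings are tempting, and the documents do not support them:

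- **That the protocol contradicts itself on the safety population.** Protocol 10.3.1 says "the efficacy, health outcomes, and safety analyses will be conducted on the modified intent-to-treat (mITT) population", but that sentence opens by allowing for exceptions. Protocol 10.3.4 then assigns safety data to the safety population. This is a default with a stated exception.
- **That an assumed early drop-out rate gives the chance of harm.** It would give the chance of any early loss. The documents differ only for an early loss with safety data, which is less frequent and for which they give no rate.
- **That the review of Cohort A before 4 mg is affected.** SAP 6.16.1 does not tie the DMC outputs to this population. The DMC chair also has access to SAEs reported to regulators (protocol 9.4.8.2).
- **That the as-randomised rule is a SAP departure, or affects every dosing error.** The rule is in the protocol as well. Missed or extra tablets of the assigned treatment cause no misclassification.

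**Conclusion.** The discrepancy is real and narrow. For one kind of patient, dosed, lost at the first postbaseline visit and with postbaseline safety data, the SAP reverses the protocol's inclusion rule without giving a reason. If it happens once and that patient had an event, an observed rate of 8.3% on 2 mg or 5.0% on 4 mg becomes zero, and the upper confidence limit falls by 10.0 or 7.3 percentage points (38.5 − 28.5; 24.9 − 17.6). How often it would happen cannot be stated from the documents.

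The as-randomised safety analysis is a separate weakness shared by both documents. It matters only if a patient took another arm's treatment, and the documents give no expected number of such patients. Efficacy and power are unaffected. Both points should be corrected because the changes are small and remove an avoidable bias.

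**What to change.** 1. In SAP 6.1.1, restore the protocol's condition so that the exclusion ends as the protocol's does: "at the first postbaseline visit with no safety post-baseline data". Alternatively, include every randomised patient who took at least one dose. Under either option, delete the provision that sends these patients' data only to a listing or profile, so that they enter the safety tables and tests.
2. Tabulate safety by treatment actually received for patients who took another arm's treatment, and state in advance how mixed exposure is classified.

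**Cost.** The first change is SAP wording only if the protocol's condition is restored. Including all dosed patients would go beyond both current definitions, so protocol 10.2 would also need aligning. It may dilute rates slightly, because a patient with no follow-up then enters a denominator. The second change needs SAP wording and a change to protocol 10.2. Protocol 10.3.1 requires an amendment only when a principal feature changes; otherwise the change and its justification can be given in the clinical study report.

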6.1.2. Definition of Baseline and Postbaseline Measures

Baseline will be defined as the last available value before the first dose of investigational product for both efficacy and safety analyses. In most cases, this will be the measure recorded at Week 0 (Visit 3). Change from baseline will be calculated as the visit value of interest minus the baseline value.

Postbaseline measurements are collected after study drug administration through Visit 7 (Week 12) or an early discontinuation visit.

6.1.3. Analysis Methods

The primary analysis for all continuous efficacy and health outcome variables will use a mixed-effects models for repeated measures (MMRM) with [REDACTED]

[REDACTED] An unstructured covariance matrix will be used to model the within-patient variance-covariance errors. If the unstructured covariance matrix results in a lack of convergence, the heterogeneous Toeplitz covariance structure, followed by the heterogeneous autoregressive covariance structure will be used. The Kenward-Roger method will be used to estimate the denominator degrees of freedom. Type III tests will be used for all the statistical comparisons; the 90% confidence interval (CI) will also be reported. The LS mean difference, standard error, p-value, and CI will also be reported. Treatment group comparisons at specific study visits will be tested using the t-test obtained from the MMRM results. Data will be censored as described in Section 6.3.

The primary analysis for all categorical efficacy and health outcome variables will use a logistic regression analysis [REDACTED]

[REDACTED] The p-value and 90% (unless otherwise specified) CI for the odds ratio from the logistic regression model will be used for primary statistical inference. When logistic regression sample size requirements are not met, (<5 responders in any category for any factor), the p-value from the Cochran-Mantel-Haenszel (CMH) test with [REDACTED]

In addition, all primary and secondary continuous efficacy and health outcome variables will use analysis of covariance (ANCOVA) models [REDACTED]

[REDACTED] and cohort in the model as a supplementary analysis. Type III sums of squares for the least-squares mean (LSM) will be used for the statistical comparison of treatment groups, and the LSM difference, standard error, p-value and 90% CI will also be reported. The last observation carried forward (LOCF) approach will be used to impute missing data.

All safety data will be descriptively summarized by treatment groups and analyzed using the safety population.

Treatment-emergent adverse event (TEAEs) are defined as AEs that first occurred or worsened in severity after the first dose of study treatment. The number of TEAEs as well as the number and percentage of patients who experienced at least 1 TEAE will be summarized using the Medical Dictionary for Regulatory Activities (MedDRA) for each system organ class (or a body system) and each preferred term by treatment group. SAEs and AEs that lead to discontinuation of investigational product and discontinuation from the study will also be summarized by treatment group. The Fisher exact test will be used to perform comparisons between the baricitinib and placebo groups.

All clinical laboratory results will be descriptively summarized by treatment group. Individual results that are outside of normal reference ranges will be flagged in data listings. Quantitative clinical hematology, chemistry, and urinalysis variables obtained at the baseline and postbaseline visits will be summarized as changes from baseline by treatment group and analyzed using analysis of covariance (ANCOVA) with treatment and baseline value in the model. The significance of within-treatment group changes from baseline will be evaluated by testing whether or not the treatment group least-squares mean (LSM) changes from baseline are different from zero; the p-value and standard error for the LSM change will be displayed. Differences in LSM will be displayed, with the p-value associated with the LSM comparison to placebo and a 95% CI on the LSM difference also provided. Treatment-emergent high/low for categorical laboratory safety analyses will also be produced. Categorical variables, including the incidence of abnormal values and incidence of AEs of special interest, will be summarized by frequency and percentage of patients in corresponding categories. Shift tables will be presented for selected measures.

Observed values and changes from baseline (predose or screening if predose is missing) for vital signs and physical characteristics will be descriptively summarized by treatment group and visit. Change from baseline to postbaseline in vital signs and body weight will be analyzed using ANCOVA with treatment and baseline value in the model.

The incidence and average duration of investigational product interruptions will be summarized and compared descriptively among treatment groups.

